However, obesity could also adversely affect asthma via other inflammatory and oxidative mechanisms beyond NOS uncoupling, such as greater Th1 polarization, and increased pro-inflammatory airway leptin and cytokine levels (8, 9). It is plausible that other signaling processes can be modulated, or be susceptible to modulation, in parallel with reduced airway NO, to worsen asthma severity. Therefore, more pleiotropic pharmacologic strategies that can impact multiple inflammatory and metabolic pathways may be useful for improving the health of obese asthmatics. To do this, we propose a novel approach, which includes oral nitrite + nitrate (NO2 + NO3) termed oxides of nitrogen (NOx) + conjugated linoleic acid (CLA) supplementation. CLA is an 18 carbon, 2 double bond-containing unsaturated fatty acid (18:2, n-6) and has been shown to reduce bronchial hyperresponsiveness in overweight or obese asthmatics (10). CLA is readily nitrated (addition of an NO2 group to a double bond) by the nitrite/nitric oxide derived species, nitrogen dioxide, producing a fatty acid nitro-alkene product with broad anti-inflammatory effects, including partial peroxisome proliferator-activated receptor gamma (PPAR $\gamma$ ) agonist activity, blocking TH17-related pathways, nuclear factor- $\kappa$ B (NF- $\kappa$ B) inhibition and Nuclear factor (erythroid-derived 2)-like 2 (Nrf2) activation (11-14). In addition to the anti-

inflammatory effects of CLA, NOx supplementation can be beneficial to obese asthmatics by increasing NO airway bioavailability (15).

[figure not shown]
**We hypothesize that in obese asthmatics treatment with NOx + CLA is well tolerated, safe and will increase eNO while reducing airway oxidative stress.** Allied with this, we will define whether supplementing with this bioactive mediator modifies the airway microbiome, and reduces airway inflammation.

**Specific Aim 1.** To determine whether treatment with NOx + CLA will increase exhaled NO and reduce airway oxidative stress in adult obese asthmatics. To do this, participants will receive 8 weeks of open label treatment with NOx (Sodium nitrate 1000 mg + Sodium nitrite 20 mg/day) + 3,000 mg/day of CLA.

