#### Sodium nitrite and stable isotope labeled sodium N nitrite

Standard sodium nitrite will be supplied as capsules for daily oral administration at the dose strength of 20 mg (study dose: 20 mg). The Joint Food and Agriculture Organization (FAO)/World Health Organization (WHO) Expert Committee on Food Additives (JECFA) proposed an Acceptable Daily Intake (ADI) for sodium nitrite, which corresponds to 0.1 mg/kg of body weight. Using the ADI for sodium nitrite (0.1 mg/kg of body weight) and a body weight of 95 kg, the calculated ADI of sodium nitrite would be 9.5 mg. Much higher doses, of oral sodium nitrite solutions ranging between 140-380 mg are well tolerated acutely with minimal side effects characterized by short-term nausea and headaches, and mild transient reductions in blood pressure with concomitant increase in heart rate. Based on the Joint FAO/WHO ADI for nitrite, the fact that this dose has been approved by the FDA for studies in humans, it is believed that a safe and tolerated dose for sodium nitrite is 20 mg (~0.2 mg/kg body weight per day for a 95 kg subject). This dose selection is roughly equivalent to 2.1 times the ADI.

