#### Sodium nitrate and stable isotope labeled sodium N nitrate

Standard sodium nitrate will be supplied as capsules for daily oral administration at the dose strength of 500 mg (study dose: 1,000 mg). In a recent study, single dose potassium nitrate capsule ingestion in healthy adult volunteers in doses of 2,424 mg KNO3 (or 1,488 mg nitrate ion) and 1,212 mg KNO3 (or 744 mg nitrate ion) resulted in dose dependent reductions in BP over a 24 hour period without adverse effects (35). Current studies from this group are on-going with long term therapy for hypertension. Short term dietary supplementation with sodium nitrate at 0.1 mmol/kg of body weight per day divided up over 3 times daily for 3 days has been studied by Lundberg et al (36-38). The daily nitrate dose administered corresponds to the amount found in 100-300 grams of nitrate-rich vegetables such as spinach, beetroot or lettuce. Many of these studies demonstrated that dietary nitrate reduced systolic and diastolic blood pressures, mean arterial pressure (MAP), and oxygen cost during physical exercise and improved mitochondrial

efficiency without adverse effects. Several human studies have examined the effect of single ingestion (35, 39), 6 day(40, 41) and 15 day (42) supplemental courses of nitrate in the form of beetroot juice on blood pressure in healthy adults. Systolic (SBP), diastolic (DBP) and mean MAP were significantly reduced with beetroot juice in these trials with no adverse events noted (35, 39-42).

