**Potential Toxicity:** For nitrate, some toxicity studies suggest a positive association with risk of non-Hodgkin lymphoma, gastric and colon cancers with years of exposure. However, these were mostly studies with weak study design and limited strength of evidence. Other case-control studies and cohort studies, which provide stronger evidence, have found no increased risk of human cancer with increasing nitrate intake from diet or drinking water after multivariate adjustment. Taking all studies together, the CONTAM panel (Contaminants in the Food Chain) of the European Food Safety Authority (EFSA) reports evidence does not suggest that nitrate intake from diet or drinking water is associated with increased cancer risk (43). In addition, there is no clear evidence of an effect of nitrate or nitrite on non-cancer human health effects. In the current study, we will use much lower doses of nitrite and nitrate than used safely in any of these studies. Our sodium nitrate of 1gm represents a nitrate ion dose (i.e. 744 mg) that is less than the nitrate ion dose (i.e. 933 mg) associated with 1.488 gm of potassium nitrate used by Webb and colleagues. This medication will be provided by [name], under IND (115,926).

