- The research coordinator will contact the subject 24-48 hours prior to Visit 3 in order to verify the medication withhold and readiness for the bronchoscopy procedure.
- Pt arrives to CTRC – MUH after an 8 hour fast
- Urine pregnancy test in females of child-bearing potential (i.e. women who are not at least 1 year post-menopausal or who have not undergone a surgical sterilization procedure).
- A physical exam will be completed
- The subject must have used less than 16 puffs of albuterol in the last 48 hours in order to proceed with bronchoscopy procedures
- Pre – bronchoscopy spirometry (pre- and post-bronchodilator) (safety assessment)
- Asthma Control Questionnaire (ACQ)& pre-bronchoscopy safety checklist
- Tongue scrape x microbiome
- Bronchoscopy for a) brushings , b) BAL, c) endobronchial biopsies; d) microbiome
- Blood work for metabolic syndrome ( fasting blood glucose, insulin levels, serum creatinine) lipid profile (HDL, triglycerides, total cholesterol, LDL and VLDL), CBC with differential, and Hgb A1C.

- Plasma collection
- Urine collection X Prostaglandin D2 (PGD2) metabolites and isoprostanes
- Exhaled NO (No food, drink (other than water), or strenuous exercise 1 hour prior to visit)
- Stool x microbiome
- Post bronchoscopy spirometry
- Dispense study drug supply- 4 week supply
- Distribute study Diary Card and review instructions

Phone call visit T1 (2 weeks after Visit 3)

- Review diaries & compliance
- ACQ
- Review any concerns and health care utilization

Visit 4 (4 weeks after Visit 3)

- Short Physical Exam
- Review of diaries and compliance
- Niox Mino (No food, drink (other than water), or strenuous exercise 1 hour prior to visit)
- Pre and Post spirometry
- ACQ & ACT
- Dispense 4 week supply of study drug

Visit 4A (if necessary)

If it is determined by the study coordinator at Visit 4 that the subject has not taken at least 75% of the study drug, the coordinator will provide a 1 week supply of the study drug and ask the subject to return to the Asthma Institute for a compliance check (visit 4A). If the subject is not compliant at Visit 4A, the subject will be withdrawn from the study. If the subject has improved compliance after 1 week, the remaining 3 week supply of the study drug will be dispensed.

Phone call visit T2 (6 weeks after Visit 3)

- Review diaries & compliance
- ACQ
- Review any concerns and health care utilization

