#### Visit 5 (after 8 weeks of treatment)

- ACQ
- Urine pregnancy test in females of child-bearing potential
- Exhaled nitric oxide test
- Brief physical exam
- Methacholine testing- This is a common test often used to confirm a diagnosis of asthma. Methacholine is a chemical that causes the airways to react (narrow) and is easily reversed with the administration of albuterol. Prior to the test, a urine pregnancy test will be performed on women of childbearing potential and a blood pressure reading will be taken. An exhaled nitric oxide test and a brief physical exam will also be performed. The challenge test consists of inhaling very low, but increasing doses of methacholine through a nebulizer to assess how quickly the airways narrow. Spirometry (focusing on the FEV-1) will be performed approximately 30 and 90 seconds after each dose to look for changes in lung function. If/when a 20% decrease in spirometry (FEV-1) is observed the challenge test will be stopped. Multiple measures are in place to perform this test safely and comfortably. Subjects will receive albuterol after the test is done.
- Patient is instructed to take Nitrogen 15 sodium nitrate and 15 sodium nitrite in substitution of regular NOx supplements (same dose) with food approximately 12 h prior to bronchoscopy. This dose is in a form that is easily observed in study samples.
- Dispense study drug supply

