### 7.3 Exclusion Criteria

- 1) Respiratory tract infection within the last 4 weeks;
- 2) Oral or systemic CS burst within the last 4 weeks;
- 3) Asthma-related hospitalization within the last 2 months;
- 4) Asthma-related ER visit within the previous 4 weeks;
- 5) Significant or uncontrolled concomitant medical illness including (but not limited to) heart disease, cancer, diabetes;
- 6) History of ICU admission/intubation due to asthma in the past year;
- 7) More than three systemic corticosteroid requiring asthma exacerbations in the past year;
- 8) Current statins use (statins lower ADMA levels), patients may stop and re-enroll after 2 weeks of stopping statins;
- 9) Positive pregnancy test;
- 10) Intolerance or allergy to the intervention drugs;
- 11) Current or recent participation (within the past 30 days) in an investigational treatment study;
- 12) Unable or unlikely to complete study assessments or the study intervention (i.e. bronchoscopy) poses undue risk to patient in the opinion of the Investigator;
- 13) Any kind of oral nitrates such as nitroglycerin or already taking supplements in this study

- 14) Systemic steroid dependent asthma (no daily oral steroids- short term therapy for asthma exacerbation is permitted)
- 15) Chronic renal failure (creatinine  $\geq 2.0$ ) at screening (associated with higher ADMA levels)- self-reported and/or verified by medical records.
- 16) Use of mouthwash containing chlorhexidine (lowers NO) within 1 week prior to screening and throughout the study.
- 17) Untreated sleep apnea
- 18) Hgb A1C  $\geq 7$ - self-reported and/or verified by medical records.
- 19) Daily use of PPI's (Proton Pump Inhibitor) or H2 Blockers for GERD (it is permitted to take on an occasional basis- no more than 1x per week. If participants wash out of these meds for 1 week, they can enroll)
- 20) Use of biologics for asthma/allergies unless there is a 4 month washout prior to enrollment
- 21) Drug and/or alcohol abuse for  $\geq 1$  year
- 22) Breastfeeding
- 23) Any other condition and/or situation that causes the investigator to deem a subject unsuitable for the study (e.g. due to expected study medication non-compliance, inability to medically tolerate the study procedures, or a subject's unwillingness to comply with study-related procedures.

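### Dietary nitrate is neither standardised nor recorded before exhaled NO and nitrate/nitrite measurements, although the protocol's own figures make it a sizeable source relative to the study dose

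*Combined protocol and SAP*

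**What the plan says.** Exhaled NO is measured at all six visits. Section 6 gives the rule at Visit 4 as "Niox Mino (No food, drink (other than water), or strenuous exercise 1 hour prior to visit". The same 1-hour condition is printed at Visits 1, 3 and 6, and Visits 3 and 6 also follow an 8-hour fast. Visit 5 lists only "Exhaled nitric oxide test", with no food condition, and Visit 2 does the same.

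Among the exclusions in Section 7.3, number 13 covers "Any kind of oral nitrates such as nitroglycerin or already taking supplements in this study", and number 16 covers chlorhexidine mouthwash because it reduces NO. Neither mentions diet. A diary card is handed out at Visit 3, but no dietary content is described.

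The study dose is "Sodium nitrate 1000 mg + Sodium nitrite 20 mg/day", with CLA. In Section 5.3 the nitrate rationale describes cited studies of "Short term dietary supplementation with sodium nitrate at 0.1 mmol/kg of body weight per day", split over three times a day for 3 days, and adds: "The daily nitrate dose administered corresponds to the amount found in 100-300 grams of nitrate-rich vegetables such as spinach, beetroot or lettuce".

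Exhaled NO is in the primary analysis (Section 8.3), as a matched pre/post comparison in one open-label group. Plasma and urine nitrate and nitrite are secondary outcome (b) (Section 4.2).

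**The concern.** The trial's hypothesis is that oral nitrate and nitrite raise airway NO through a route other than NO synthase. On that hypothesis, nitrate from vegetables acts in the same direction as the intervention. The protocol accepts that an everyday exposure can shift NO, since it controls chlorhexidine, but it leaves out the dietary source that its own dose rationale describes.

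Two things are at stake. If prior-day intake varies from visit to visit, it adds noise to a change measured in a planned 12 participants. If intake shifts systematically once participants know that they are taking a nitrate product, the shift enters the estimated treatment effect, and there is no concurrent control to remove it.

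**Working it through.** **Inputs.** Study dose 1,000 mg sodium nitrate per day (Section 1). Vegetable-equivalent dose 0.1 mmol/kg/day (Section 5.3). Molar masses: sodium nitrate 84.995 g/mol, nitrate ion 62.005 g/mol. Body weight in the cited studies: not given, so 60-95 kg is assumed. The upper end is the protocol's own reference, "a body weight of 95 kg", which it uses in the nitrite section and not for those studies.

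**Step 1, the plan's own figure.** The protocol states: "Our sodium nitrate of 1gm represents a nitrate ion dose (i.e. 744 mg". Recomputed: 1,000 / 84.995 = 11.77 mmol, and 11.77 x 62.005 = about 730 mg. The stated 744 mg is about 2% higher. The comparison below uses sodium nitrate mass on both sides, so this does not affect it.

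**Step 2, size of the dietary source.** Sodium nitrate (mg) = 0.1 x weight (kg) x 84.995.

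| Assumed weight in cited studies | Sodium nitrate per day | Share of 1,000 mg |
|---|---|---|
| 60 kg | 510 mg | 51% |
| 80 kg | 680 mg | 68% |
| 95 kg | 807 mg | 81% |

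Because 100-300 g is a threefold range, a 100 g portion supplies between a third of the amount and all of it: from 510 / 3 = 170 mg to 807 mg. For contrast, Section 5.3 puts dietary CLA at 15-174 mg per day against 3,000 mg, at most 174 / 3,000 = 6%.

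**Step 3, do the food rules deal with it?**

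| Visits | Food rule before exhaled NO | Plasma and urine biomarkers |
|---|---|---|
| 1, 4 | 1 hour | no |
| 2, 5 | none printed | no |
| 3, 6 | 1 hour, after an 8-hour fast | yes |

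None of these reaches food eaten the day before. The protocol expects its own labelled nitrate and nitrite, taken before the Visit 6 bronchoscopy, to be visible in the samples. Section 6 (Visit 5) puts that dose about 12 hours before and the Section 5.2 footnote puts it at 24 hours; these two passages must be reconciled. On either timing, nitrate taken before an 8-hour fast is expected to leave a trace. A label can be detected at low levels, so this shows persistence and not how much remains.

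**Step 4, effect on the paired comparison.** Each participant's change is drug effect + change in diet contribution + residual. A stable diet cancels. Random variation raises the variance of the change; a systematic shift moves its mean.

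Section 8.1 says there are no preliminary exhaled NO data, so the effect cannot be sized. Purely as illustration, for a paired t-test with n = 12 and two-sided 0.05:

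- Noise: a standardised change of 1.03 has 90% power. If diet adds a fraction f to the variance of the change, the standardised change becomes 1.03 / sqrt(1 + f). Power is 83%, 76% and 63% for f = 0.25, 0.5 and 1.0.
- Drift: with no drug effect, a systematic diet shift of 0.25 or 0.5 SD of the change gives a significant result in 12% or 35% of trials instead of 5%.

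The values of f and of the shift are assumptions, not estimates.

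**The case against.** The case on the other side is substantial. This is a proof-of-concept pilot, and its conditions are already matched before and after treatment: Visits 1 and 4 share a rule, as do 2 and 5, and 3 and 6. Pairing removes stable differences in diet. The cited nitrate studies are reported for blood pressure, oxygen cost and mitochondrial efficiency, not exhaled NO. At Visit 6 the isotope label separates the labelled dose from other sources.

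Most of this stands as a limit on size, but it does not close the gap. Matched rules do not control what was eaten the day before, and pairing does not remove within-person change. The label does not help exhaled NO or total nitrate and nitrite.

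Several stronger readings are tempting, and the documents do not support them:

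- A reader might apply 0.1 mmol/kg to heavier trial participants and conclude that vegetables match the full study dose. A given amount of vegetables holds a fixed amount of nitrate whatever the eater weighs. The relevant weight is that of the cited studies' subjects.
- A reader might infer that one serving is enough. The protocol describes a whole day's dose in three parts.
- A reader might infer that a baseline reading could sit near treated exposure. One day's intake is not comparable with 8 weeks of daily nitrate, nitrite and CLA, and no kinetics are given.
- A reader might infer that diet will produce a false positive. That needs a systematic pre-to-post change, and nothing in the documents shows one.

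**Conclusion.** The gap is real: no section restricts, standardises or records dietary nitrate. The vegetable amount that the protocol cites corresponds to roughly 50-80% of the daily study nitrate dose by intake, assuming cited-study weights of 60-95 kg. The protocol does not state this closeness; it follows by arithmetic.

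The likely consequence is added noise in the exhaled NO change and, at Visits 3 and 6, in plasma and urine nitrate and nitrite. Section 8.3 does not name the visits that form the exhaled NO pair, so Visits 2 and 5, with no printed food rule, may contribute. Drift in diet is a possibility that the design could not detect, not a demonstrated bias. The size of either effect on exhaled NO cannot be computed from the documents. The point justifies an inexpensive change and does not invalidate the trial.

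**What to change.** 1. Give the same written instruction before every exhaled NO and sampling visit, before and after treatment: avoid beetroot products and nitrate-rich leafy vegetables from the day before.
2. Print the 1-hour food rule at Visits 2 and 5 as well.
3. Record prior-day intake with one diary or checklist item at each visit. The diary card starts at Visit 3, so the pre-treatment visits need a checklist item.
4. Repeat the pre/post exhaled NO and nitrate/nitrite comparisons as a sensitivity analysis by recorded intake. Do not exclude participants on baseline plasma nitrate or nitrite. Plasma is collected only at Visits 3 and 6, so it cannot flag the other visits, and such exclusion would select on an outcome variable in a very small sample.

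The cost is an instruction sheet, one recorded item and a short amendment, with minor participant burden and an occasional rescheduled reading.

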#### Visit 5 (after 8 weeks of treatment)

- ACQ
- Urine pregnancy test in females of child-bearing potential
- Exhaled nitric oxide test
- Brief physical exam
- Methacholine testing- This is a common test often used to confirm a diagnosis of asthma. Methacholine is a chemical that causes the airways to react (narrow) and is easily reversed with the administration of albuterol. Prior to the test, a urine pregnancy test will be performed on women of childbearing potential and a blood pressure reading will be taken. An exhaled nitric oxide test and a brief physical exam will also be performed. The challenge test consists of inhaling very low, but increasing doses of methacholine through a nebulizer to assess how quickly the airways narrow. Spirometry (focusing on the FEV-1) will be performed approximately 30 and 90 seconds after each dose to look for changes in lung function. If/when a 20% decrease in spirometry (FEV-1) is observed the challenge test will be stopped. Multiple measures are in place to perform this test safely and comfortably. Subjects will receive albuterol after the test is done.
- Patient is instructed to take Nitrogen 15 sodium nitrate and 15 sodium nitrite in substitution of regular NOx supplements (same dose) with food approximately 12 h prior to bronchoscopy. This dose is in a form that is easily observed in study samples.
- Dispense study drug supply

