**Specific Aim 2.** To determine whether treatment with **NOx + CLA** can influence airway NO bioavailability, as well as oxidative, metabolic and inflammatory pathways. Participants will undergo pre and post-treatment bronchoscopies to obtain airway epithelial cells, bronchoalveolar lavage fluid (BALF) and endobronchial biopsies. Peripheral blood and urine will also be collected at each of these bronchoscopies. To do this, we will compare the following pre and post intervention endpoints: a) total CLA levels, nitrite/nitrate in urine and plasma, and NO2-cLA levels in BALF, plasma, and urine; b) NFκB and Nrf2 pathways in peripheral blood monocyte cells (PBMC) and alveolar macrophages, c) leptin/adiponectin in BAL and plasma, d) plasma ADMA e) airway microbiome in BAL f) airway xanthine oxidase (XO) activity from endobronchial biopsies (as an airway oxidative stress source), g) TH17: BAL fluid/cells: IL-17 levels, mRNA, flow cytometry, h) metabolomics study to look at where N is incorporated other than NO2-cLA; to do this, participants will take same dose of nitrate and nitrite N heavy isotopes, the day prior to the second bronchoscopy.

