#### **4.2 Secondary Outcomes**

To determine whether, compared to baseline, treatment with NOx + CLA can:

- a) Increases eNO levels
- b) Quantify the concentrations of nitrate/nitrite in plasma and urine, free cLA in plasma, and NO2-cLA in BALF, plasma, and urine
- c) Reduce airway oxidation and inflammation
  - a. Western and RTPCR NF-κB and Nrf2 pathways in airway macrophages and PBMCs
  - b. Airway leptin and adiponectin
  - c. Proportion of airway TH-17 cells/responses

- d) Airway XO activity determined in endobronchial biopsies
- e) Measurement of  $^{15}\text{NO}_2\text{-cLA}$  and endogenous  $^{14}\text{NO}_2\text{-cLA}$  in urine, plasma and BAL
- f) Decrease production of anion superoxide in fresh airway epithelial cells;
- g) Mitochondrial ROS production and bioenergetics in fresh and cultured airway epithelial cells. As a potential source for airway / epithelial oxidative stress

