### 5.2 Description of the Study Design

Potential subjects will be recruited from the Asthma Institute registry and the CTSI registry, and throughout the community at large. After an initial screen visit, those who sign the consent and meet eligibility will proceed to have methacholine testing; subjects with a > 12% bronchodilation in FEV1, or achieving a 20 % reduction in FEV1 from baseline (PC20) after methacholine, will receive **NOx + CLA** for a period of 8 weeks.

\* 15Nox dose will be taken 24 hours prior to V6 bronchoscopy

\*\*An additional visit might be needed in some participants to perform pre- and post-spirometry after an adequate medication withhold

Prior to treatment, participants will undergo a baseline bronchoscopy at UPMC Montefiore, after which they will be instructed to begin taking the assigned intervention for 8 weeks. At the completion of the treatment period, participants will undergo a second methacholine challenge and a final bronchoscopy.

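### At Visit 6, 14NO2-cLA is unlabelled product, not endogenous product: outcome 4.2 e follows about 8 weeks of unlabelled study nitrate and nitrite and needs relabelling

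*Combined protocol and SAP*

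**What the plan says.** Section 4.2 item e lists the measurement of 15NO2-cLA "and endogenous $^{14}\text{NO}_2\text{-cLA}$ in urine, plasma and BAL". It names no visit and no calculation.

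On exposure, Specific Aim 1 says "participants will receive 8 weeks of open label treatment with NO x" plus CLA, at 1,000 mg sodium nitrate, 20 mg sodium nitrite and 3,000 mg CLA per day. Section 5.2 starts this after the baseline bronchoscopy: "after which they will be instructed to begin taking the assigned intervention for 8 weeks". Section 5.3 distinguishes the standard nitrate and nitrite from the isotope-labelled forms.

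On the label, Visit 5 in Section 6 says "Patient is instructed to take Nitrogen 15 sodium nitrate and 15 sodium nitrite in substitution of regular NOx supplements (same dose". Specific Aim 2 item h likewise says "participants will take same dose of nitrate and nitrite" as heavy isotopes, on the day before the second bronchoscopy. More study drug is dispensed at Visit 5, and Visit 6 falls 24 hours to 1 week later. No washout, half-life, enrichment calculation or dietary nitrate restriction is given.

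**The concern.** The word *endogenous* in 4.2 e assumes that anything carrying 14N was made by the body independently of the study drug. That would be true if all study nitrate and nitrite carried 15N. Here only the last dose does. NO2-cLA formed from any earlier study dose also carries 14N, and the assay cannot tell it from the body's own product or from product of dietary nitrate.

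NO2-cLA is central to the rationale: Section 1 presents the nitrated fatty acid as the product with broad anti-inflammatory effects. If the Visit 6 14N value is reported under its present name, any carried-over drug product is counted as endogenous, the supplement's contribution is understated, and a rise in 14N could be mistaken for more endogenous nitration.

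**Working it through.** The plan states no figure for this outcome, so there is none to reproduce. The check has two parts.

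**1. Which visit, and what is in the pool.**

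- 15N is first taken shortly before the Visit 6 bronchoscopy, so a 15N/14N pair exists only at Visit 6.
- Unlabelled daily doses before it: 8 weeks × 7 days = 56. If dosing continues between Visits 5 and 6, as the Visit 5 dispensing suggests, there are somewhat more.
- 14N at Visit 6 = endogenous + dietary + carried-over study doses. 15N at Visit 6 = product of the labelled dose.

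**2. How large the carry-over could be.** The half-life *h* of the product is an assumption, because the documents give none. Assume also first-order loss, equal doses every 24 h, and one labelled dose replacing the last of them. At time *t* after the labelled dose:

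- labelled signal ∝ 2^(−t/h)
- *j*-th earlier dose ∝ 2^(−(t+24j)/h)
- with r = 2^(−24/h), carry-over ÷ labelled signal = r + r² + … = r/(1−r)
- carry-over as a share of all drug-derived product = r

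| Assumed h | r (share of drug-derived product) | r/(1−r) (relative to labelled signal) |
|---|---|---|
| 6 h | 2^(−4) = 0.0625 | 0.0625/0.9375 = 7% |
| 12 h | 2^(−2) = 0.25 | 0.25/0.75 = 33% |
| 24 h | 2^(−1) = 0.50 | 0.50/0.50 = 100% |
| 72 h | 2^(−1/3) = 0.794 | 0.794/0.206 = 385% |

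Summing exactly 56 earlier doses gives the same ratios. The share falls below 5% only if h < 24/log2(20) = 24/4.32 ≈ 5.6 h.

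**Sensitivity.** If NO2-cLA forms from a precursor with a half-life of 4 to 8 h, the unlabelled share of drug-derived product is:

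- 2–13% for a product half-life of 2 h
- 26–44% for 12 h
- 51–65% for 24 h
- 80–86% for 72 h

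**Timing of the labelled dose.** In the simple model *t* cancels, so the result is the same whether the labelled dose is taken "with food approximately 12 h prior to bronchoscopy" (Visit 5) or as in the note in Section 5.2, "15Nox dose will be taken 24 hours prior to V6 bronchoscopy". Those two statements contradict each other and must be reconciled, but that is a separate matter. What does matter is the gap *g* between the last unlabelled dose and the labelled one, which is not stated. The ratio is then 2^(−g/h)/(1−r). For h = 12 h, g = 12 h gives 0.5/0.75 = 67% and g = 36 h gives 0.125/0.75 = 17%, against 33% for 24 h.

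The model sizes carry-over against the labelled signal only. The percentage error in a reported endogenous level also depends on the endogenous and dietary levels, which the documents do not give.

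**The case against.** The strongest reply is that this is one adjective in a one-line list of measurements. No section plans a 14N/15N ratio or any split by source. A drug-free comparison is already planned: Section 4.2 compares with baseline, item b measures NO2-cLA in BALF, plasma and urine, Aim 2 item a makes it a pre/post endpoint, and Section 8.3 tests secondary outcomes by matched pre/post comparison. With a short half-life, carry-over could also be negligible.

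Much of this stands. A reader might infer that carry-over makes it impossible to separate drug-derived from other product. The documents do not support that, since it depends on a half-life they do not state. Nor does cumulative intake over 56 doses measure what is still present at Visit 6.

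A reader might also infer that the Aim 2 h tracing is compromised. It is not: it asks where 15N from the labelled dose goes, and earlier 14N doses create no false 15N products.

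What does not stand is the idea that the pre/post comparison rescues the word *endogenous*. Visit 3 precedes CLA as well as NOx, and CLA at 3,000 mg/day supplies more of the substrate that is nitrated. A rise in 14N from Visit 3 to Visit 6 could therefore be endogenous nitration of extra substrate, diet or carry-over.

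**Conclusion.** The label in 4.2 e is wrong as written, whatever the half-life, because nothing in the design keeps product of earlier study doses out of the 14N pool. Reading 4.2 e as a Visit 6 measurement is an inference, but the only one under which a 15N/14N pair exists.

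The size of the carry-over is unknown. Under first-order loss and once-daily dosing it runs from about 7% of the labelled signal (6 h half-life) to 385% (72 h). It could be negligible or dominant, and the plan neither states nor measures what would decide which. The documents support saying that the Visit 6 split cannot be relied on to separate sources; they do not support saying that separation is impossible.

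The 15N value remains valid as product of the labelled dose. The point affects what one secondary outcome may conclude. It does not affect the primary analysis, the safety monitoring or the sample size.

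**What to change.** In Section 4.2 item e:

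- Replace the endogenous label with *unlabelled 14NO2-cLA (endogenous, dietary and earlier study doses)*.
- Define 15NO2-cLA as product of the labelled dose.
- Name the Visit 3 level as the pre-treatment reference, taken before both NOx and CLA.
- Report the already planned pre/post comparison as the Visit 6 minus Visit 3 change in total (14N + 15N) NO2-cLA. The total needs no split by source.
- State that neither the Visit 6 14N/15N split nor a rise in 14N will be interpreted as endogenous versus supplement-derived formation.

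Aim 2 h needs no change. The cost is rewording, with no new visit, sample or dose. Aim 2 already has blood and urine collected at each bronchoscopy. The visit lists mention urine only for PGD2 metabolites and isoprostanes, so it is worth confirming that an aliquot is kept for NO2-cLA. The small downside is giving up a claim to measure endogenous formation during treatment.
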